## RESEARCH ATTRIBUTES

0 unresolved  
comment(s)

Indicate the items below that apply to your research. Depending on the items applicable to your research, you may be required to complete additional forms or meet additional requirements. Contact the ORI [contact]) if you have questions about additional requirements.

Not applicable

Check All That Apply

- Academic Degree/Required Research
- Alcohol/Drug/Substance Abuse Research
- Biological Specimen Bank Creation (for sharing)
- Cancer Research
- CCTS-Center for Clinical & Translational Science
- Certificate of Confidentiality
- Clinical Research
- Clinical Trial - Phase 1
- Clinical Trial
- Collection of Biological Specimens for internal banking and use (not sharing)
- Community-Based Participatory Research
- Deception
- Educational/Student Records (e.g., GPA, test scores)
- Emergency Use (Single Patient)
- Gene Transfer
- Genetic Research
- GWAS (Genome-Wide Association Study) or NIH Genomic Data Sharing (GDS)
- Human Cells, Tissues, and Cellular and Tissue Based Products
- Individual Expanded Access or Compassionate Use
- International Research
- Planned Emergency Research Involving Exception from Informed Consent
- Recombinant DNA
- Registry or data repository creation
- Stem Cell Research
- Suicide Ideation or Behavior Research
- Survey Research
- Transplants
- Use, storage and disposal of radioactive material and radiation producing devices
- Vaccine Trials

For additional requirements and information:

- [Cancer Research \(MCC PRMC\)](#)
- [Certificate of Confidentiality](#) (look up "Confidentiality/Privacy...")
- [CCTS \(Center for Clinical and Translational Science\)](#)
- [Clinical Research](#) (look up "What is the definition of....")
- [Clinical Trial](#)
- [Collection of Biological Specimens for Banking](#) (look up "Specimen/Tissue Collection...")
- [Collection of Biological Specimens](#) (look up "Specimen/Tissue Collection...")
- [Community-Based Participatory Research](#) (look up "Community-Engaged...")
- [Data & Safety Monitoring Board \(DSMB\)](#)

\*For Medical IRB: [Service Request Form](#) for CCTS DSMB

- [Data & Safety Monitoring Plan](#)
- [Deception\\*](#)

\*For deception research, also go to the E-IRB Application Informed Consent section, checkmark and complete "Request for Waiver of Informed Consent Process"

- [Emergency Use \(Single Patient\) \[attach Emergency Use Checklist\]](#) (PDF)
- [Genetic Research](#) (look up "Specimen/Tissue Collection...")
- [Gene Transfer](#)
- [HIV/AIDS Research](#) (look up "Reportable Diseases/Conditions")
- [Screening for Reportable Diseases \[E2.0000\]](#) (PDF)
- [International Research](#) (look up "International & Non-English Speaking")
- [NIH Genomic Data Sharing \(GDS\) Policy](#) (PDF)
- [Planned Emergency Research Involving Waiver of Informed Consent\\*](#)

\*For Planned Emergency Research Involving Waiver of Informed Consent, also go to the E-IRB Application Informed Consent section, checkmark and complete "Request for Waiver of Informed Consent Process"

- [Use, storage and disposal of radioactive material and radiation producing devices](#)

## FUNDING/SUPPORT

0 unresolved  
comment(s)

If the research is being submitted to, supported by, or conducted in cooperation with an external or internal agency or funding program, indicate below all the categories that apply. 

Not applicable

## Check All That Apply

- Grant application pending
- (HHS) Dept. of Health & Human Services
  - (NIH) National Institutes of Health
  - (CDC) Centers for Disease Control & Prevention
  - (HRSA) Health Resources and Services Administration
  - (SAMHSA) Substance Abuse and Mental Health Services Administration
- (DoJ) Department of Justice or Bureau of Prisons
- (DoE) Department of Energy
- (EPA) Environmental Protection Agency
- Federal Agencies Other Than Those Listed Here
- Industry (Other than Pharmaceutical Companies)
- Internal Grant Program w/ proposal
- Internal Grant Program w/o proposal
- National Science Foundation
- Other Institutions of Higher Education
- Pharmaceutical Company
- Private Foundation/Association
- U.S. Department of Education
- State

Other:

Click applicable listing(s) for additional requirements and information:

- [\(HHS\) Dept. of Health & Human Services](#)
- [\(NIH\) National Institutes of Health](#)
- [\(CDC\) Centers for Disease Control & Prevention](#)
- [\(HRSA\) Health Resources & Services Administration](#)
- [\(SAMHSA\) Substance Abuse & Mental Health Services Administration](#)
- Industry (Other than Pharmaceutical Companies) [[IRB Fee Info](#)]
- [National Science Foundation](#)
- [\(DoEd\) U.S. Department of Education](#)
- [\(DoJ\) Department of Justice or Bureau of Prisons](#)
- [\(DoE\) Department of Energy Summary and Department of Energy Identifiable Information Compliance Checklist](#)
- [\(EPA\) Environmental Protection Agency](#)

Specify the funding source and/or cooperating organization(s) (e.g., National Cancer Institute, Ford Foundation, Eli Lilly & Company, South Western Oncology Group, Bureau of Prisons, etc.):

This research is supported from K01 funds of UC Davis Coinvestigator [name]. We are contracted to provide lab analysis. [name] (IRB Applicant, UK) is the PI and does not require salary support.

## Add Related Grants

If applicable, please search for and select the OSPA Account number or Electronic Internal Approval Form (eIAF) # (notif #) associated with this IRB application using the "Add Related Grants" button.  
If required by your funding agency, upload your grant using the "Grant/Contract Attachments" button.

[Add Related Grants](#)

[Grant/Contract Attachments](#)

The research involves use of Department of Defense (DoD) funding, military personnel, DoD facilities, or other DoD resources. (See [DoD SOP](#) and [DoD Summary](#) for details)

Yes  No

Using the "attachments" button (below), attach applicable materials addressing the specific processes described in the DoD SOP.

[DOD SOP Attachments](#)

Additional Certification: (If your project is federally funded, your funding agency may request an Assurance/ Certification/Declaration of Exemption form.) Check the following if needed:

Protection of Human Subjects Assurance/Certification/Declaration of Exemption (Formerly Optional Form – 310)

[Assurance/Certification Attachments](#)

## OTHER REVIEW COMMITTEES

0 unresolved  
comment(s)

If you check any of the below committees, additional materials may be required with your application submission.

Does your research fall under the purview of any of the other review committees listed below? [If yes, check all that apply and attach applicable materials using the attachment button at the bottom of your screen.]

Yes  No

## Additional Information

- Institutional Biosafety Committee
- Radiation Safety Committee
- Radioactive Drug Research Committee
- Markey Cancer Center (MCC) Protocol Review and Monitoring Committee (PRMC)
- Graduate Medical Education Committee (GME)
- Office of Medical Education (OME)

- [Institutional Biosafety Committee \(IBC\)](#) - Attach required IBC materials
- [Radiation Safety Committee \(RSC\)](#) - For applicability, see instructions and attach form
- [Radioactive Drug Research Committee \(RDRC\)](#)
- [Markey Cancer Center \(MCC\) Protocol Review and Monitoring Committee \(PRMC\)\\*\\*](#) - Attach MCC PRMC materials, if any, per instructions.
- [Office of Medical Education \(OME\)](#)
- [Graduate Medical Education Committee \(GME\)](#)

## Attachments

**\*\* If your study involves cancer research, be sure to select "Cancer Research" in the "Research Attributes" section.** ORI will send your research protocol to the Markey Cancer Center (MCC) Protocol Review and Monitoring Committee (PRMC). The [MCC PRMC](#) is responsible for determining whether the study meets the National Cancer Institute (NCI) definition of a clinical trial and for issuing documentation to you (the investigator) which confirms either that PRMC approval has been obtained or that PRMC review is not required. Your IRB application will be processed and reviewed independently from the PRMC review.

## ADDITIONAL INFORMATION/MATERIALS

0 unresolved  
comment(s)

Do you want specific information inserted into your approval letter?  Yes  No

## Approval Letter Details:

If you wish to have specific language included in your approval letter (e.g., serial #, internal tracking identifier, etc...), type that language in the box below exactly as it should appear in the letter. The text you enter will automatically appear at the top of all approval letters, identical to how you typed it, until you update it. Don't include instructions or questions to ORI staff as those will appear in your approval letter. **If these details need to be changed for any reason, you are responsible for updating the content of this field.**

## Additional Materials:

If you have other materials you would like to include for the IRB's consideration, check all that apply and attach the corresponding documents using the Attachments button below.

- Detailed protocol
- Dept. of Health & Human Services (DHHS) approved protocol (such as NIH sponsored Cooperative Group Clinical Trial)
- Other Documents

## Protocol/Other Attachments

Attach Type	File Name
Other	58219 [name] IR22.pdf

NOTE: [Instructions for Dept. of Health & Human Services \(DHHS\)-approved protocol](#)

If you have password protected documents, that feature should be disabled prior to uploading to ensure access for IRB review.

To view the materials currently attached to your application, click "All Attachments" on the left menu bar.

## Statistical Analysis Plan – 58219

Statistical Analysis: Data analyses were performed using SPSS v28 (IBM Corp. 2021) with graphing via SPSS and Prism GraphPad (v9.5.1). Using an intention-to-treat approach, we performed univariate and multivariable analysis for primary and secondary outcomes as change from baseline per individual/group and between groups. We used Pearson's (for normally distributed data) or Spearman's (for non-normally distributed data) correlation to examine relationships between continuous variables, Pearson's chi square and Fisher's exact tests between categorical variables, and independent t-test or Mann-Whitney U test between binary and continuous variables as appropriate. Paired samples t-tests or Wilcoxon matched-paired sign-rank test were used for paired data. Continuous variables are presented here as mean with standard deviation (if normally distributed) as mean  $\pm$  SD or median with interquartile range (if not normally distributed) as median, IQR, while categorical variables are presented with counts and percentages. An alpha-level of 0.05 was used to determine significance. All enrolled participants who continued study activities through at least the first month were analyzed regardless of loss to follow up.

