### Data collection:

Monthly anthropometrics for mother, infant, and child. These include infant weight, length and maternal and child weight, height/length, and mid-upper arm circumference.

Enrollment and exit quantitative surveys including but not limited to Food Frequency Questionnaire from which we will calculate Dietary

Diversity Score.

Mother, infant and child finger or finger/ heel stick for hemoglobin and capillary blood collection at study enrollment and exit.

Mother, infant and child feces collection at study enrollment and exit.

Daily recording by parent in provided diary of daily moringa percent consumption, incidence of diarrhea, diagnosis by health professional of medical condition in mother, infant, or child.

Lactating Women:

24 hour volume of breastmilk at study enrollment and exit

Breastmilk sample collection (est. 5ml) at study enrollment and exit

We would like to complete one more anthropometric measurement (weight and length) of enrolled infants in the next few months; this is 8-12 months from study start.

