### Phase B)

Participants regularly receive postnatal appointments at their health center for routine child check with health center staff. During this visit, our trained study personnel will enroll the participants and separately perform anthropometrics (weight, height or length, mid upper-arm circumference), collect blood, fecal, and breastmilk sample, and distribute study supplies. At monthly visits (month 1, 2, exit visit at month 3), followup will occur at the participant's study site. At these visits, study staff will perform anthropometrics, review porridge and/or moringa consumed, review parental diary, distribute study supplies, and at end visit will again collect blood, fecal, and breastmilk samples as applicable. Compliance with porridge-moringa ratio will be assessed by review of parent recorded amount consumed in the diary and direct visualization of percentage of porridge and leaf powder remaining prior to distribution. This will occur via verbal recall for parents identifying as illiterate.

Biological samples of mothers, infants and children (blood by heel stick or finger stick and stool) will be collected by trained study personnel at the presenting health center on enrollment and exit (3 months). Hemoglobin will be assessed by Hemoccue® utilizing a capillary (heel or finger) stick with direct readout. Capillary blood by heel or finger stick will be transferred to special paper and dried appropriately to create Dried Blood Spots by a standardized process and/or stored in aliquot containers. Fecal collection will occur on the day of monthly presentation to the health center, or kits and instructions will be given to caregivers and the stool collected by study personnel in the participant's village. Hemoglobin will be recorded to the nearest 0.1 g/dL by Hemoccue®. Stool, breastmilk, and blood samples will be immediately chilled and transported to Kenya Medical Research Institute Lab (KEMRI) in Kisumu, processed, and stored at -80 degree C freezers until transport. Samples will then be shipped on dry ice to the University of Kentucky or to the contracted laboratory for analysis. Breastmilk will be transported to Eurofin Laboratories or the laboratory of analysis. Breastmilk volume will be performed at enrollment and exit by 24 hour breastmilk volume pumped by hand pump that we supply and measured with the milk subsequently fed to the infant.

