Head circumference: A standard measuring tape will be extended from the broadest part of forehead to the broadest part of the back of the head for infants. A mean of three consecutive measurements will be recorded to the nearest 0.1cm.

Standardization: For infants and children, weight for age, weight for length/height, and length/height for age will be compared to WHO standard deviation tables or Z scores and assigned their Z score. Wasting is low weight for length/height; stunting is low length/height for age; underweight is low weight for age. These are all measures of undernutrition. Mild undernutrition is defined for any of those parameters as <-1 to and including <-2; moderate undernutrition is <-2 to and including -3; severe undernutrition is <-3. Infants or children with Severe Acute Malnutrition defined as severe wasting (weight or length for height <-3), and/or the presence of nutritional edema will be referred to the nearest nutritional rehabilitation center for treatment as per standard WHO protocol. For mothers, Body Mass Index will be calculated (weight / height squared in metric units) and MUAC recorded.

Quality Control: Participants will be consecutively measured by the same instruments. The study coordinator will perform monthly quality control assessing variance between measurers for all measurements in order to ensure consistent measurement. Retraining and observed measurement will occur for any inconsistencies. Patients who do not arrive for their monthly visits will be contacted to remind them if contact information is available, and then visited at home if unable to come to the health center.

Vitamin A: serum retinol binding protein will survey infant vitamin A levels as an efficient measure of vitamin A at the individual level.

(46,47) Other assays of vitamin A are more informative at the population level. Measurement of the systemic inflammatory marker CRP (C-reactive protein) will allow for assessment of Vitamin A with and without correction for inflammation.

Iron: low hemoglobin is a proxy of childhood iron deficiency utilized internationally by UNICEF in LMIC. Iron levels can be measured via their transporters and intermediate forms. Calculation of a transferrin receptor-ferritin index from ferritin and soluble transferrin receptor will lessen the impact of fluctuations in ferritin from inflammation.(48,49)

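### The SAP promises univariate and multivariable analysis of change but names only unadjusted between-arm tests for continuous outcomes; the enrolment-adjusted regression should be the main comparison

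*Combined protocol and SAP*

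**What the plan says.** The SAP is a single paragraph. On primary and secondary outcomes it says: "we performed univariate and multivariable analysis for primary and secondary outcomes as change from baseline per individual/group and between groups". The tests it lists for continuous outcomes are:

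- between arms: "independent t-test or Mann-Whitney U test between binary and continuous variables as appropriate";
- within arms: "Paired samples t-tests or Wilcoxon matched-paired sign-rank test were used for paired data".

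It names no regression model, no covariate and no rule on whether the univariate or the multivariable result is the main one. No other visible section of the protocol supplies these.

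Enrolment values are planned for most continuous outcomes. Under Study Design, Data collection, the protocol lists "Mother, infant and child finger or finger/ heel stick for hemoglobin and capillary blood collection at study enrollment and exit" and "Mother, infant and child feces collection at study enrollment and exit". Research Procedures, Phase B repeats that blood and stool "will be collected by trained study personnel at the presenting health center on enrollment and exit (3 months"), and it places anthropometry at the enrolment visit and at months 1, 2 and 3. Infant and child weight and length or height "will be compared to WHO standard deviation tables or Z scores and assigned their Z score" (Data Collection & Research Materials, Standardization).

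Breastmilk is less clear. Data collection lists "Breastmilk sample collection (est. 5ml) at study enrollment and exit" and Phase B agrees, but the Aim 3 breastmilk text in Data Collection & Research Materials lists a sample at exit only.

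**The concern.** Subtracting the enrolment value is not the same as adjusting for it. A change-score comparison fixes the slope on the enrolment value at 1, whereas regression estimates it. When enrolment and exit values are only moderately correlated, a slope of 1 over-corrects and adds noise. In a pilot of this size that noise matters.

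The second difficulty is that two legitimate analyses of each outcome are promised and nothing says which one counts. They can fall on opposite sides of 0.05, and the SAP judges significance at that level.

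Using change as the outcome is not itself the error. If the enrolment value is in the model, modelling change or the exit value gives the same arm estimate.

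**Working it through.** **Inputs from the documents.** 50 dyads and 50 children per arm (Phase B, Pilot RCT); 100 per arm (Study Design); a maximum of 104 subjects (Project Information); 82 infants per arm needed and 100 to be recruited (Subject Children, Section 2); alpha 0.05 (SAP), taken here as two-sided. The plan gives no precision or power figure for a continuous outcome, so there is none to reproduce. Its only sizing calculation is for binary stunting, which this point does not touch.

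**Assumptions, none given in the documents.** Correlation r between enrolment and exit of 0.3 to 0.9; effect of 0.5 or 0.3 exit SDs; normal data; equal SDs unless stated.

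**Same estimate from change or exit value.** If exit − enrolment = a + b·arm + c·enrolment, then exit = a + b·arm + (c+1)·enrolment. The arm coefficient b is unchanged.

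**Variance.** With exit SD 1 and enrolment SD k:

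- change score: 1 + k² − 2rk
- adjusted: 1 − r²
- difference: k² − 2rk + r² = (k − r)², never negative

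So in large samples adjustment is never less precise. At k = 1 the ratio is (1 − r²) / [2(1 − r)] = (1 + r)/2:

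| r | Ratio adjusted/change | Adjusted n per arm with the precision of 50 per arm by change score |
|---|---|---|
| 0.3 | 0.65 | 32.5 |
| 0.5 | 0.75 | 37.5 |
| 0.7 | 0.85 | 42.5 |
| 0.9 | 0.95 | 47.5 |

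With unequal SDs:

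- r = 0.5: k = 0.8 gives 0.75/0.84 = 0.89; k = 1.25 gives 0.75/1.3125 = 0.57.
- r = 0.7: k = 0.8 gives 0.51/0.52 = 0.98; k = 1.25 gives 0.51/0.8125 = 0.63.

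Estimating the slope costs little: in simulation (40,000 replicates) at 26 per arm the ratios were 0.658, 0.766, 0.868 and 0.963, that is 1–2% above the formula. Both estimators averaged the true effect.

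**Power.** Noncentral t with noncentrality d·√(n/(2V)), and 2n − 2 (change) or 2n − 3 (adjusted) degrees of freedom. Example: n = 50, d = 0.5, r = 0.5. For change V = 1, so noncentrality is 0.5·√25 = 2.50; adjusted V = 0.75, so 2.50/√0.75 = 2.89.

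Power at 0.5 SD, change score vs adjusted:

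| n per arm | r = 0.3 | r = 0.5 | r = 0.7 | r = 0.9 |
|---|---|---|---|---|
| 26 (104 read as 52 dyads) | 32 vs 46% | 42 vs 53% | 63 vs 70% | 98 vs 98% |
| 41 (50 less 18%) | 47 vs 65% | 61 vs 73% | 82 vs 88% | over 99% both |
| 50 | 55 vs 74% | 70 vs 82% | 89 vs 93% | over 99% both |
| 100 | 85 vs 96% | 94 vs 98% | over 99% both | over 99% both |

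The 26 and 41 rows rest on further assumptions: that the 104 are all dyad members, and that the step from 82 to 100 is all loss to follow-up. At 0.3 SD and 50 per arm, power is 24 vs 34%, 32 vs 40%, 48 vs 55% and 91 vs 93% at r = 0.3, 0.5, 0.7 and 0.9.

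**How often the two analyses disagree on p<0.05** (simulation, 50 per arm):

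| Effect | r = 0.3 | r = 0.5 | r = 0.7 | r = 0.9 |
|---|---|---|---|---|
| 0.5 SD | 24% | 16% | 6% | 0% |
| 0.3 SD | 19% | 17% | 13% | 3% |
| none | 5% | 5% | 4% | 2% |

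With no true effect, counting whichever result is significant gives a false-positive rate of 7.5, 7.3, 6.9 and 6.2% per outcome, against a nominal 5%.

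**Skewed markers** (simulated lognormal, log-SD 1, effect 0.5 log-SD, 50 per arm), power at r = 0.3 / 0.5 / 0.7:

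- Mann-Whitney on the raw change: 52 / 67 / 85%
- rank-based adjusted regression: 71 / 78 / 90%
- log-scale adjusted regression: 73 / 81 / 93%

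All are about 100% at r = 0.9. With no effect, rejection rates lie between 4.6 and 5.6%.

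**The case against.** The strongest reply is that the plan is being read at its worst. The multivariable analysis may already contain the enrolment value, and the t-test and Mann-Whitney test are listed generically, not as the headline arm comparison. Precision is lost only if the unadjusted test is the headline or the multivariable model omits the enrolment value. That is fair, but the text does not settle it, and the team can do so in one sentence.

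Other points stand in part:

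- **The choice is between two valid estimators.** True. The case for adjustment rests on precision, not on bias.
- **The SAP is in the past tense.** A main analysis chosen after results are seen does not cure selective choice. In that case the regression belongs beside the unadjusted result, labelled as added later.
- **A month-3 regression needs a month-3 value.** The SAP analyses those who continued through at least month 1, so later losses drop out. The plan's own change-to-exit test has the same gap.
- **This is a pilot, and the only sized outcome is binary.** True, yet Aim 2 tests hypotheses on growth, vitamin A and iron. The attached outcome table is not visible, so the ranking of outcomes cannot be judged.
- **The size depends on an unknown r.** True, which is why a range is given. The 26- and 41-per-arm rows are the weakest; the 50 and 100 rows use the protocol's own numbers.

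**Conclusion.** The concern holds. The SAP leaves the main between-arm analysis of continuous outcomes undecided and names only unadjusted tests, although the enrolment values needed for a more precise analysis are already planned.

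The harm is lost precision and an open choice, not bias. At equal SDs the variance saving from adjustment is 35% at r = 0.3 and 5% at r = 0.9. At 50 per arm and 0.5 SD that is worth 18, 12 and 4 power points at r = 0.3, 0.5 and 0.7, and practically nothing at 0.9. At 26 per arm both analyses are underpowered for r of 0.7 or less, and adjustment recovers 7 to 14 points. All of this rests on assumed r, SD ratio, effect size and distribution. It does not apply to binary stunting.

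**What to change.** For each continuous outcome with an enrolment value (anthropometry, haemoglobin, blood and stool markers), state in the SAP that the main between-arm analysis is a regression of the month-3 value, or equivalently the change, on arm and enrolment value. Fit it separately for mothers, infants and children aged 6–59 months, and report the arm difference with its 95% confidence interval. Keep the unadjusted t-test or Mann-Whitney test as supportive and the within-arm paired tests as descriptive. List any further covariates. For skewed markers, ranks or a transformation are both workable; state which is used.

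Apply this to breastmilk only once the sections listing enrolment and exit samples are reconciled with the Aim 3 text listing exit alone.

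The cost is a few sentences and one regression per continuous outcome in each group, with no new data. If results already exist, it is a reanalysis, to be labelled as added afterwards and shown beside the unadjusted result.

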**Phase B) Pilot RCT**

Inclusion criteria: lactating women of at least 18 years of age and their exclusively breastfed infants within 30 days of delivery with informed consent. Children 6-59 months who are orally feeding with caregiver informed consent.

Exclusion criteria: regular maternal consumption of moringa in the month prior to study enrollment, receipt and consumption of food supplementation program, or inability to feed orally; for infant, significant congenital disease, inability to feed orally. For child: inability to feed orally or refusal to eat porridge (>3 days consecutively).

We anticipate enrolling up to 50 mother-infant dyads in each of two arms and 50 children in each of two arms.

We propose starting enrollment as soon as all ethical approvals obtained, personnel hired, and study supplies obtained; there is no additional sample composition of subjects. This study targets women and infants as breastfeeding infants have the potential to receive the greatest benefit from moringa leaf supplementation to their lactating mothers.

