**SECTION 2. Assessment and Evaluation of the Risks**

For details, refer to the UK IRB's [Policy on Children in Research](#).

A. Provide justification for the participation of children as research subjects in your study.

We are investigating the effect to their infants of moringa oleifera leaf supplementation to breastfeeding mothers. Infants are thus required participants

B. Has this research been conducted in adults?  Yes  No

If yes, is there any indication that the proposed research would benefit, or at least not be harmful to children?

Multiple generations of traditional use of moringa oleifera by adults, children, animals; many studies utilizing moringa oleifera leaf with no significant safety concern to breastfeeding mother or children

C. Indicate how many children you propose to enroll in the study: 320

**Note:** Whenever possible, involve the fewest number of children necessary to obtain statistically significant data which will contribute to a meaningful analysis relative to the purpose of the study.

Justify this number:

In the United States as an example of a mostly well-resourced population, stunting prevalence in children under five years is 3.5% (UNICEF data from last census 2016).(44) In comparison, in a 2019 cross-sectional survey of Pamoja CBO recipient population in Kisumu (unpublished data, Pamoja CBO 2019) stunting prevalence is 25% in children <5 years. This is comparable to the most recent national level Kenyan data of the region that contains Kisumu (Nyanza region) from the 2014 Kenyan National Demographic Health Survey showing a stunting prevalence of 24.9% in children <5 years of age.(45) We hypothesize that we will see a 75% reduction in stunting prevalence (<-2 LAZ) at 3 months of age in children with moringa-supplemented breastmilk versus controls. We think that moringa supplementation will

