increase breastmilk volumes thus increasing infant growth and may lead to improved intestinal health leading to increased absorption of nutrients consumed. Thus, we estimate a change from estimated 25% stunting prevalence to 6.5% stunting; in comparison, this is still double the prevalence of stunting in children under five years in the United States (3.5% UNICEF data 2016). At 80% power, this would require a sample size of 82 infants in each arm. Due to concern for loss to follow up and a possibility of a smaller effect than estimated, we aim to recruit 100 infants in each arm if external funding is obtained. That is 200 infants. We also estimate 50 children 6-59 months in each arm, that is 100 children. We also estimate 10-20 children trying moringa and placebo for the acceptability study. That is a total of 320 children.

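### The trial is sized on stunting prevalence at 3 months, but the SAP analyses all outcomes as change from baseline and never specifies the powered comparison

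*Combined protocol and SAP*

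**What the plan says.** The growth hypothesis and the only sample-size calculation are in the section on children as subjects (Section 2, item C). It predicts a "75% reduction in stunting prevalence (<-2 LAZ) at 3 months of age in children with moringa-supplemented breastmilk versus controls", puts figures on this ("we estimate a change from estimated 25% stunting prevalence to 6.5% stunting"), and concludes: "At 80% power, this would require a sample size of 82 infants in each arm". The endpoint is binary, is read at one time point and is compared between arms.

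The Statistical Analysis Plan – 58219 is a single paragraph. It states: "we performed univariate and multivariable analysis for primary and secondary outcomes as change from baseline per individual/group and between groups". It names no primary outcome and no time point, does not mention stunting, does not say what change means for a yes/no variable, and does not define the multivariable model. It also lists chi-square and Fisher's exact tests for categorical variables, and adds: "An alpha-level of 0.05 was used to determine significance".

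The Data Collection section lists an attached file of timeline and outcome tables. That file is not part of the documents available for review.

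**The concern.** Each infant is measured at enrolment and at month 3. For the sample size, an infant stunted at both visits is an event. Under a per-individual change rule, the same infant scores 0; only new stunting (+1) and resolved stunting (-1) register. An analyst could compare month-3 status, change in stunting status, or change in continuous LAZ, and claim to follow the SAP each time. These analyses can give different p-values from the same data.

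Two things are at stake. The hypothesis used to justify enrolling infants has no prespecified test. And the stated power belongs to an analysis that the SAP does not specify, so the power of the analysis actually run cannot be read from the plan.

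**Working it through.** **Inputs from the documents.** Control 25%, moringa 6.5%, 80% power, 82 per arm, alpha 0.05. Sidedness is not stated; two-sided is assumed.

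**Step 1: the plan's own figure.** With p1 = 0.25, p2 = 0.065 and mean 0.1575:

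n = [1.96·√(2·0.1575·0.8425) + 0.842·√(0.25·0.75 + 0.065·0.935)]² / 0.185² = (1.010 + 0.419)² / 0.0342 = 59.7, so 60 per arm.

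The continuity correction gives 71. One-sided versions give 47 and 58. None gives 82; 90% power two-sided without correction gives 80, which is close. Conversely, power at 82 is Φ[(0.185·√82 − 1.010)/0.498] = Φ(1.336) = 90.9%. Exact enumeration gives 92.3% for chi-square and 89.0% for Fisher. So 82 is conservative for the powered comparison.

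**Step 2: what the change score estimates.** Let b be the proportion stunted at enrolment, equal in both arms by randomisation. The expected between-arm difference in change is (p1 − b) − (p2 − b) = p1 − p2 = 0.185. The target is the same as for month-3 status; only the variance differs.

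**Step 3: variance and power.** Let π be the probability of being stunted at both visits. In an arm with exit prevalence p, the score −1/0/+1 has variance v = b + p − 2π − (p − b)². Power = Φ[0.185/√((v1 + v2)/n) − 1.96].

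Assumptions not in the documents: bivariate-normal LAZ, correlation r of 0.5 to 0.7 between enrolment and exit LAZ, and b from 5% to 25%.

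Example, b = 25% and r = 0.5: π is 0.1203 (control) and 0.0411 (moringa), so v1 = 0.2594 and v2 = 0.1986. At n = 82, 0.185/√(0.4580/82) = 2.475, and power is Φ(0.515) = 69.7%.

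For month-3 status the same formula uses p(1 − p) in each arm: 0.185/√(0.2483/82) = 3.362, and power is Φ(1.402) = 92.0%.

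| Stunted at enrolment (assumed) | Change in status, 82/arm, r = 0.5 | r = 0.7 |
|---|---|---|
| 25% | 69.7% | 78.2% |
| 15% | 78.3% | 86.2% |
| 10% | 83.5% | 89.9% |
| 5% | 88.6% | 92.4% |

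At b = 25%, between 0.1203/0.25 = 48% (r = 0.5) and 0.1504/0.25 = 60% (r = 0.7) of control infants stunted at exit were already stunted at enrolment, and would score 0.

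If the correlation is instead set between the yes/no indicators, over 0 to 0.7 where attainable, with b from 5% to 25%, power at 82 ranges from 56% to 98%.

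**Step 4: change in continuous LAZ.** Under normality, 25% to 6.5% is a shift of 1.514 − 0.674 = 0.84 SD. With r = 0.5 the change has SD 1, so power at 82 is Φ[0.84/√(2/82) − 1.96], over 99%. It is higher still at r = 0.7.

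**Step 5: 50 per arm.** The Study Population section says: "We anticipate enrolling up to 50 mother-infant dyads in each of two arms and 50 children in each of two arms". At 50 per arm, month-3 status itself has 72.5% power by the Step 1 formula and 76.5% by exact chi-square.

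**The case against.** The strongest reply is that the SAP does not exclude the powered comparison. It refers to change per individual or group, names chi-square and Fisher's exact tests, and reports categorical variables as counts and percentages; arm by month-3 stunting fits that description. The −1/0/+1 score is one reading, and the SAP does not define it. The unseen outcome table may settle the matter. This stands as far as it goes: the comparison is unspecified, not forbidden. But naming a test does not name the variable it is applied to, and the preceding sentence of the SAP puts all outcomes in change form. Nor does the group reading avoid the issue: with complete pairs, the between-arm difference in change in prevalence equals the difference in mean individual scores.

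A reader might infer that the stated 80% power is not delivered at 82 per arm. The documents do not support that. The clear shortfall appears when 25% are assumed stunted at enrolment, but that 25% comes from a survey of children aged 0 to 59 months, while these infants enrol within 30 days of delivery. At 5 to 10% the change analysis stays above 80%. At 100 per arm ("we aim to recruit 100 infants in each arm if external funding is obtained") the Step 3 formula gives 78 to 86% even with 25% stunted at enrolment. Nor is it true in general that a change analysis has less power, since change in continuous LAZ has more.

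A reader might also blame the change wording for low power at 50 per arm. Month-3 status already falls short there, so that is a separate matter of enrolment numbers.

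**Conclusion.** The mismatch holds. The sample size rests on month-3 stunting prevalence between arms; the SAP states change from baseline for everything and never specifies that comparison. Read per individual, the rule usually loses precision: from about 92% power to between 70% and 92% at 82 per arm, under a bivariate-normal LAZ model with r of 0.5 to 0.7 and 5 to 25% stunted at enrolment. At 5% and r = 0.7 the two analyses tie. The enrolment prevalence and the correlation are assumptions, so power below 80% is possible but not demonstrated. Under randomisation both analyses target the same 18.5-point difference, so the defect is one of alignment and precision, not bias. Separately from that model, the documents' own inputs show that 82 is not the 80%-power figure.

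**What to change.** In the SAP:

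- State that stunting, and likewise wasting and underweight, is compared between arms as status (z below −2) at the month-3 visit, preferably adjusted for the baseline z-score, which is already collected. Name the test or model.
- Restrict change from baseline to continuous measures. Tabulate new, resolved and persistent stunting descriptively.

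In the sample-size justification, tie the power statement to this comparison and correct it: about 60 per arm for 80% power (71 with continuity correction), or about 91% power at 82. State whether the time point is 3 months of age or the month-3 visit; with enrolment up to 30 days after delivery, the two can differ by up to 30 days.

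The cost is a sentence or two in the SAP, a corrected power statement and no new data. The downside is that change in stunting status becomes descriptive only. The SAP is written in the past tense, so if results have already been seen, the clarification should be dated and reported as such.
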